## **PROTOCOL SUMMARY**

Registry Title	Post-Market Registry of the GORE ® VIABAHN ® VBX Balloon Expandable Endoprosthesis Implanted in Peripheral Vessels		
Short Title	EXPAND Registry		
Protocol Number	VBX 17-04		
Sponsor	W. L. Gore & Associates, Inc. Medical Products Division [contact]		
Local Representative	Gore Authorized Representative W. L. Gore & Associates B.V. [name]		
Registry Design	Prospective, multicenter, observational registry		
Registry Objective	The primary objective of the VBX 17-04 registry is to collect post-market safety and performance data of the GORE ® VIABAHN ® VBX Balloon Expandable Endoprosthesis (VBX Stent Graft) in peripheral vessels in patients who require interventional treatment		
Primary Endpoint	
 
A composite of any of the following events through 30 days post treatment.
 
Procedural Success
 
Freedom from VBX Stent Graft-related Serious Adverse Event (SAE)
 
		
Se condary Endpoints	
 
VBX Stent Graft-related death within 30 days post-treatment
 
Procedural-related death within 30 days post-treatment
 
Procedural-related SAE within 30 days post-treatment
 
VBX Stent Graft patency (primary, primary assisted, secondary) through 30 days post-treatment
 
VBX Stent Graft patency (primary, primary assisted, secondary) through five years post-treatment
 
VBX Stent Graft-related SAE through five years post-treatment
 
VBX Stent Graft-related death through five years post-treatment
 
VBX Stent Graft-related death through five years post-treatment
 
Loss of VBX Stent Graft integrity through five years post-treatment
 
Limb salvage through five years post-treatment
 
		
Patient Population	Patients with peripheral lesions or needing preservation of peripheral vessels that are amenable with VBX Stent Graft treatment.		

Number of Patients	Two hundred eighty (280) implanted patients with the VBX Stent Graft. No one site can contribute more than 35% of the registry's population (98 patients).	
Number of Sites	A maximum of 20 sites located in Europe	
Coordination PI		
Key Inclusion Criteria	
 
Age ≥ 18 years.
 
Signed informed consent form.
 
Intend for no other stents to be placed in the same peripheral vessel(s) targeted for VBX Stent Graft placement
 
	
Key Exclusion Criteria	
 
Known hypersensitivity to heparin or a previous incident of Heparin-Induced Thrombocytopenia (HIT) type II.
 
Life expectancy < 12 months due to comorbidities.
 
Treatment would be for de novo iliac occlusive disease
 
Use of the VBX Stent Graft is for the treatment of aortic coarctations
 
Use of the VBX Stent Graft in the coronary, pulmonary, carotid, vertebral, isolated infrarenal aortic or vena cava vessels
 
	
Expected Time to Complete Enrollment	28 Months	
Expected time of each study patient to complete the study	60 Months	
Total expected duration of the study	88 Months	
Schedule of Events	All registry events will be performed per standard medical practice at each participating site.	
Vendor		

### LIST OF ABBREVIATIONS

AE ADE AIOD	Adverse Event Adverse Device Effect Aortoiliac Occlusive Disease
	Arteriovenous
CRES	Covered Balloon Expandable Stent
CDMS	Clinical Data Management System
CE	Conformité Européenne
CEC	Clinical Event Committee
CERAB	Covered Endovascular Reconstruction of Aortic Bifurcation
CRF	Case Report Form
CRO	Contract Research Organization
СТА	Computed Tomographic Angiography
EC	Ethics Committee
EDC	Electronic Data Capture system
eCRF	Electronic Case Report Form
GCP	Good Clinical Practice
HIT	Heparin-Induced Thrombocytopenia
IB	Investigator's Brochure
ICF	Informed Consent Form
ICH	International Conference on Harmonization
IFU	Instructions for Use
mm	Millimeters
PI	Principal Investigator
SAE	Serious Adverse Event
U.S.	United States
USADE VBX Stent Graft	Unanticipated Serious Adverse Device Effect GORE® VIABAHN® VBX Balloon Expandable Endoprosthesis

### DEFINITIONS

Adverse Event: Any untoward medical occurrence, unintended disease or injury, or untoward clinical signs (including an abnormal laboratory finding) in patients, users, or other persons, whether or not related to the investigational medical device.

Adverse Device Effect: Adverse event related to the use of an investigational medical device.

**Clinical Investigation Plan:** A set of documents that describes the rationale, objectives, design and proposed analysis, methodology, monitoring, and the plan for the conduct of a clinical investigation. These documents may include the protocol, monitoring plans, and statistical analysis plans.

**Device Deficiency:** Inadequacy of a medical device with respect to its identity, quality, durability, reliability, safety, or performance. Device deficiencies include malfunctions, use errors, and inadequate labeling.

**Enrollment:** A patient is considered enrolled into the study once informed consent has been signed and dated.

Serious Adverse Event: An adverse event that led to death, serious deterioration in the health of the patient or led to fetal distress, fetal death, or a congenital abnormality or birth defect. Defined in more detail in Section 9.

Serious Adverse Device Effect: An adverse device effect that has resulted in any of the consequences characteristic of a serious adverse event.

**Unanticipated Serious Adverse Device Effects:** Serious adverse device effect which by its nature, incidence, severity, or outcome has not been identified in the current version of the protocol, Investigator Brochure (IB) or Instructions for Use (IFU).

PR	отос	OL SUMMARYi	ii
LIS	TOF	ABBREVIATIONS	v
DEF	INITI	ONS	vi
1.	Intro	duction	1
	1.1. 1.2.	Background Registry Rationale	1 1
2.	Regi	stry Objectives	2
	2.1.	Primary Objective(s)	2
3.	Regi	stry Design	3
	3.1. 3.2.	Description of Registry Design         Registry Endpoint(s)	3 3 3 4 5
4.	Stud	y Population	5
	4.1. 4.2. 4.3.	Description of Population 4.1.1. Treatment Population Characterization Inclusion Criteria Exclusion Criteria	5 6 7 7
5.	Regi	stry Procedures / Reporting	7

### 1. Introduction

### 1.1. Background

Seminal papers by Dotter and Parodi introduced the medical community to the ability to treat atherosclerotic lesions that were either circulation-restrictive or critically-dilated in a less invasive fashion. Since the introduction of these concepts, the equipment, techniques, and products used in interventional procedures have vastly improved due to the refinement of device design and advancements in technology. Multiple professional study treatment guidelines now advocate the use of stent-grafts as the preferred or primary method to treat certain patients.

In current application, covered balloon-expandable stents (CBES) are used in a multitude of applications either within the arterial or venous systems. One of the most prominent uses of a CBES is in aortoiliac occlusive disease (AIOD). The GORE® VIABAHN® VBX Balloon Expandable Endoprosthesis (VBX Stent Graft) underwent clinical investigation of de novo lliac occlusive disease in the United States (U.S.) and New Zealand where the device performed well in all types of occlusive disease including lesions that are considered to be more severe in nature, TASC II C /  $D^{4, 5}$ . The pivotal study reported 100% technical success with a nine-month primary patency rate of 96.7% (n=98 patients). Pivotal patients will be followed for three years post-procedure. There is a reasonable expectation that some institutions may report their experiences with the VBX Stent Graft in AIOD in the near future.

Other clinical indications that may occur less frequent in the spectrum of treatment are visceral artery lesions, either iatrogenic or non-iatrogenic, that are in need for urgent, minimally invasive surgery . In these cases, the stent-graft is the primary method of lesion exclusion. There are other techniques where a peripheral CBES is paired with a thoracic, thoracoabdominal, or abdominal stent-graft to exclude an aneurysm as part of a system. The CBES component may be used through a pre-designed portal / fenestration to connect with the aortic stent or placed in parallel to the other device, sometimes called a chimney or snorkel procedure, in order to maintain perfusion to covered branch vessels.

#### 1.2. Registry Rationale

Post-market observational registries are critical to identify, collect, and analyze medical devices outcomes. Peripheral stents see usage for a broad spectrum of applications and this registry offers an opportunity to understand breakdown of usage for the VBX Stent Graft. As the nature of these registries allows for the assessment of medical device performance in a real-world setting, data collected are useful for many purposes, such as limited surveillance of marketed products, fulfillment of post-market clinical follow-up data commitments for regulatory bodies, and differential assessment of device performance from a well-controlled, clinical trial environment to that of routine medical practice.

The VBX Stent Graft leverages the stent graft design and clinical requirements of the GORE® VIABAHN® Endoprosthesis with PROPATEN Bioactive Surface. Clinical data collected from a wide range of clinical studies, registries and case studies has confirmed the long-term clinical performance of the VIABAHN® device itself The VBX 17-04 registry is designed to collect short-term procedural and clinical information, as well as safety events through five years.

Registry Device Description

The GORE® VIABAHN® VBX Balloon Expandable Endoprosthesis (VBX Stent Graft) is manufactured in Flagstaff, Arizona of the United States of America by W. L. Gore & Associates, Inc. (Gore). The device is Conformité Européenne (CE)-marked for use in peripheral vessels where an endovascular stent-graft may be warranted. The design, device sizes, and characteristics permit the use of the device in multiple pathologies.

The VBX Stent Graft consists of a 316 L surgical grade stainless steel balloon expandable stent and a fluoropolymer graft (**Figure 1**). The CBAS Heparin Surface on the VBX Stent Graft consists of stable, covalent, end-point attached heparin of porcine origin. The endoprosthesis is pre-mounted on a delivery system equipped with a balloon. The delivery system has two radiopaque balloon markers embedded in the shaft (denoting the effective balloon length) to aid in the placement of the endoprosthesis (**Figure 2**). The delivery system is compatible with 0.035" (0.89 mm) guide wires. The delivery system can be used for initial stent placement and post stent dilatation. The pre-mounted stent system is available in a variety of endoprosthesis lengths from 15 to 79 mm and in a variety of diameters from 5 to 11 mm. The pre-mounted endoprosthesis system balloon catheter is also offered in two shaft lengths. This product is supplied sterile.

Figure 1. GORE® VIABAHN® VBX Balloon Expandable Endoprosthesis

## Figure 2. GORE® VIABAHN® VBX Balloon Expandable Endoprosthesis Delivery System

More detailed device information can be found in the Instructions for Use (IFU) and Investigators Brochure (IB).

## 2. Registry Objectives

2.1. Primary Objective(s)

The primary objective of the VBX 17-04 registry is to collect post-market safety and performance data of the VBX Stent Graft in peripheral vessel in patients who require interventional treatment. This objective is based upon the need to incorporate post-approval data into the continuing evaluations of the VBX Stent Graft over its lifecycle.

## 3. Registry Design

### 3.1. Description of Registry Design

This registry utilizes a prospective, multicenter, non-randomized single-arm design to collect VBX Stent Graft clinical data in its use within the indicated peripheral vasculature but outside of *de novo* iliac occlusive disease. Data will be representative of real-world, clinical use. Real world clinical use data are integral for Gore combined with data from long-term clinical investigations and reports from medical literature, to perform continuing assessments of device performance in addition to any long-term clinical investigations as well as reports in medical journals. To ensure that registry data are representative of real world use, the registry will employ broad inclusion / exclusion criteria to ensure its observational nature.

A maximum of 20 clinical registry sites (referred to as "sites" in the remainder of this document) in Europe will participate in this observational registry. Gore will maintain an updated list of all principal investigators, site names, and addresses. This list shall be kept separately from this protocol. From all enrolled patients, the first 280 implanted patients will be evaluated for the registry." No one site can contribute more than 35% of the total patient population (98 patients). There are no pathology-specific limitations at the registry or site level. The anticipated accrual rate is approximately 10 implanted patients per month for a total accrual period of approximately 28 months based upon the rapidity of site-start-up.

Patients may be enrolled into the registry provided all inclusion and no exclusion criteria are met as specified in **Section 4**. Patients will be evaluated through hospital discharge with follow-up data collection up to 5 years post-treatment. Patients will be followed according to the regimen determined by their follow-up physician with entry into an Electronic Data Capture (EDC) system. Total estimated duration of the registry is 88 months.

- 3.2. Registry Endpoint(s)
  - 3.2.1. Definitions

The definitions in

Table 1 are provided to facilitate consistent reporting across all registry sites.

Protocol Term	Definition
Procedural Success	Technical Success (successful access, delivery, accurate deployment, and withdrawal of catheters) with patent VBX Stent Graft at end of procedure
	Primary - Uninterrupted patency with no procedures performed on or at the margins of the treated segment.
Patency 	Primary Assisted - Any procedure performed in the treated segment before thrombosis that might prevent eventual failure.
	Secondary - Any procedure that restores patency after thrombosis.

#### Table 1. Protocol Definitions

Limb Salvage	Freedom from Major Tissue Loss—extending above transmetatarsal level; functional foot no longer salvageable 	
Loss of Device Integrity	
 
Defined as any of the following:
 
Device damage that compromises device functionality (stent fractures, graft tears, cuts, holes, delamination)
 
Transient (compression) or permanent stent-graft collapse (invagination) following complete device deployment, resulting in an overall reduction in the vessel luminal diameter
 
	
Reintervention	
 
An additional unanticipated interventional or surgical procedure (including conversion to open surgery), related to the device (including withdrawal of the delivery system) or procedure. Anticipated or unanticipated status will be determined at the discretion of the investigator.
 
This includes reintervention to the VBX device used during the Index procedure and not in non-VBX treatment areas
 
	
Type I endoleak 	
 
A sealing failure at one of the attachment sites of the graft to the vessel wall providing arterial flow alongside the graft and into the perigraft space.
 
Type la- Proximal attachment site
 
Type lb- Distal attachment site
 
Type lc- Inadequate seal at distal landing zone of branch vessel device
 
	
Type II endoleak	Retrograde flow through collateral vessels into the aneurysmal sac.	
Type III endoleak	
 
Type Illa- Arterial flow from module disconnection
 
Type Illb- Arterial flow from fabric disruption
 
	
Type IV endoleak	Arterial flow through porous fabric	

### 3.2.2. Primary Endpoint

The primary endpoint of the VBX 17-04 registry is a composite of the following events reported within 30 days of treatment.

- Procedural Success
- Freedom from VBX Stent Graft-related Serious Adverse Event (SAE)

The first component, procedural success, describes the technical function of the VBX Stent Graft at the time of implant. The other component event, freedom from VBX Stent Graft-related SAE, is a description of short-term device safety. Possible endpoint events will be identified from site reports and adjudicated by a Clinical Events Committee (CEC) for reporting eligibility.

### 3.2.3. Secondary Endpoint(s)

Selected events that are illustrative of the device's potential impact to a patient from a safety perspective, overall device function described as patency or device durability captured as device integrity are the registry's secondary endpoints. Possible endpoint events will be identified from site reports with some secondary endpoints within scope of CEC adjudication.

The secondary endpoints for the VBX 17-04 registry are the following:

- VBX Stent Graft-related death within 30 days post-treatment
- Procedural-related death within 30 days post-treatment
- Procedural-related SAE within 30 days post-treatment
- VBX Stent Graft patency (primary, primary assisted, secondary) through 30 days post-treatment
- VBX Stent Graft patency (primary, primary assisted, secondary) through five years post-treatment
- VBX Stent Graft-related SAE through five years post-treatment
- VBX Stent Graft-related death through five years post-treatment
- Loss of device integrity through five years post-treatment
- Limb salvage through five years post treatment

### 4. Study Population

4.1. Description of Population

The registry has been designed with broad eligibility criteria to capture real-world VBX Stent Graft use, in multiple pathologies and in conditions needing preservation of peripheral vessels. It is anticipated that patients will generally benefit by the ability of the VBX Stent Graft to either exclude lesions from circulation or restore / ensure vessel patency to promote circulation to distal vessels or tissues. Only patients who meet all of the inclusion criteria and none of the exclusion criteria will be included in registry analyses. No vulnerable populations are included in this registry. The only exclusions to registry participation are in situations where the use of the VBX Stent Graft is contraindicated for safety, registry participation would infringe on patient rights, or that the collection of follow-up data would not have any utility.

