10.3.2. Analysis Populations

All enrolled patients meeting the inclusion / exclusion criteria and treated with the VBX Stent Graft will be included in the primary and secondary endpoint analyses.

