	 This includes reintervention to the VBX device used during the Index procedure and not in non- VBX treatment areas 			
	A sealing failure at one of the attachment sites of the graft to the vessel wall providing arterial flow alongside the graft and into the perigraft space.			
Type I endoleak	Type Ia- Proximal attachment site			
	 Type lb- Distal attachment site 			
	 Type Ic- Inadequate seal at distal landing zone of branch vessel device 			
Type II endoleak	Retrograde flow through collateral vessels into the aneurysmal sac.			
Type III andelesk	Type IIIa- Arterial flow from module disconnection			
	Type IIIb- Arterial flow from fabric disruption			
Type IV endoleak	Arterial flow through porous fabric			

Statistical Hypotheses

No formal hypothesis will be tested in the study

Sample Size Assumptions

The assumptions that provided basis for the required sample size included Clinical success of 97.1% and freedom from device or procedure related SAEs to be 93.6%

Sample Size Calculations

Two hundred eighty (280) patients will be implanted with the VBX Stent Graft across multiple pathologies. The sample size of 280 patients was considered adequate to estimate study outcomes with reasonable precision and to have sufficient subjects enrolled within each indication. The sample size was determined by Gore to characterize broad device use across device indications. In combination with strategic selection of participating registry sites, this number should be sufficient to describe the study endpoints with less than 6% margin of error.

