5.0 Clinical Event Committee

An independent Clinical Event Committee (CEC) will review safety- related, clinical events during the study to ensure the consistency of endpoints reported by the site. The VBX 17-04 CEC will be comprised of an interdisciplinary team of three members with pertinent expertise who are not directly involved in the conduct of the study.

The scope of the CEC activity includes the following:

- 1. General review and adjudication of Serious Adverse Events (SAEs) to include:
 - a. Adjudication on the SAE designation
 - b. Adjudication of the relationship of the SAE to the study device, procedure, or unrelated
- 2. Protocol Deviation review (as appropriate)
 - a. Due to the potential safety concern, protocol deviations associated with inclusion/exclusion criteria will be reviewed and the CEC will assess their risk for significant medical events that would not be expected from a subject that met all inclusion/exclusion criteria.

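### Treated patients who breach an eligibility criterion are left out of every endpoint analysis, including SAE and death, which conflicts with evaluating the first 280 implanted patients

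*Protocol*

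**What the plan says.** Two sets of statements describe who is analysed.

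**Eligible and treated only.** Protocol 4.1: "Only patients who meet all of the inclusion criteria and none of the exclusion criteria will be included in registry analyses". Protocol 10.3.2: "All enrolled patients meeting the inclusion / exclusion criteria and treated with the VBX Stent Graft will be included" in the primary and secondary endpoint analyses. SAP 6.0 ii repeats that sentence. The endpoints covered (protocol 3.2.2 and 3.2.3) include device-related SAE, procedure-related SAE, and device- and procedure-related death.

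**All implanted.** Protocol 3.1: "From all enrolled patients, the first 280 implanted patients will be evaluated for the registry". The Design Summary in SAP 2.0 says the same. The Protocol Summary gives the number as "Two hundred eighty (280) implanted patients with the VBX Stent Graft". The sample size text in both documents rests on that number: "this number should be sufficient to describe the study endpoints with less than 6% margin of error".

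The plan expects eligibility breaches. Protocol 6.3 names verification of the criteria as one of the few areas where a deviation can arise. SAP 5.0 says: "Due to the potential safety concern, protocol deviations associated with inclusion/exclusion criteria will be reviewed", with the committee to assess whether such patients carry a risk of medical events not expected in an eligible patient.

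**The concern.** The registry exists to collect post-market safety and performance data from everyday practice. A patient in whom the stent graft was used is part of that experience, whether or not a criterion was later found to be breached. Under the stated limit, a device-related SAE or death in such a patient is recorded but enters no primary or secondary endpoint rate.

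This matters most where the breached criterion concerns safe use. Exclusion 1 (heparin hypersensitivity or previous HIT type II) is described in Appendix A as a contraindication to the device. An event in such a patient is one that a post-market registry would want to count.

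Timing adds to the concern. Protocol 4.2 has the criteria evaluated at consent signature, and protocol 5.3 allows consent after the implant in an emergency. Procedural success, one of the two primary components, is then already known when eligibility is checked, so exclusion after the outcome is known is possible.

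**Working it through.** **1. Do the two sets of statements conflict?** Enrolment means signed consent (protocol Definitions and 5.5). A screen failure is an enrolled patient who does not receive the device (5.5). An implanted patient found to breach a criterion is therefore enrolled, implanted and not a screen failure. That patient counts towards the 280 in 3.1 but is removed by 4.1, 10.3.2 and SAP 6.0 ii. With no replacement rule in the text, each such patient takes the analysed number below 280.

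**2. The plan's own precision figure.** Inputs: n = 280; a margin below 6%; two-sided exact binomial 95% intervals (SAP 6.0); planning rates in SAP 2.0, "Clinical success of 97.1% and freedom from device or procedure related SAEs to be 93.6" per cent.

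- Wald half-width, 1.96 × √(p(1−p)/n), at p = 0.5: 1.96 × √(0.25/280) = 5.86 points. The stated margin reproduces.
- Exact (Clopper-Pearson) at p = 0.5: 6.01 points, over by 0.01.
- Exact at 93.6% (262/280): 90.03% to 96.15%, half-width 3.06.
- Exact at 97.1% (272/280): 94.45% to 98.76%, half-width 2.16.

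**3. Precision after exclusions.** The share of treated patients found ineligible, f, is not given. I assume 2%, 5% and 10%, so the analysed number is 280 × (1 − f).

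| f | n | exact half-width at 93.6% | exact half-width at 97.1% | Wald at p = 0.5 |
|---|---|---|---|---|
| 0 | 280 | 3.06 | 2.16 | 5.86 |
| 2% | 274 | 3.12 | 2.20 | 5.92 |
| 5% | 266 | 3.13 | 2.27 | 6.01 |
| 10% | 252 | 3.22 | 2.26 | 6.17 |

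The small irregularity at 97.1% comes from rounding to whole patients. The worst case passes 6 points, but at the planned rates the loss is at most about 0.2 points.

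**4. Possible overstatement of freedom from SAE.** Take the SAP's 93.6% as the figure in eligible patients (event rate e = 0.064) and let ineligible patients have r times that risk. The relative risk r is not given; I assume 1 to 3.

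Event rate in all treated = (1 − f) × e + f × r × e. Overstatement = f × (r − 1) × e.

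| f | r = 1 | r = 1.5 | r = 2 | r = 3 |
|---|---|---|---|---|
| 2% | 0 | 0.06 | 0.13 | 0.26 |
| 5% | 0 | 0.16 | 0.32 | 0.64 |
| 10% | 0 | 0.32 | 0.64 | 1.28 |

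(percentage points)

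Example, f = 10% and r = 3: 252 × 0.064 = 16.13 patients with an event among the eligible, and 28 × 0.192 = 5.38 among the ineligible. Together 21.50/280 = 7.68%, so freedom from SAE is 92.32% against the 93.6% that would be reported.

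The 93.6% refers to device- or procedure-related SAEs, whereas the primary component is device-related only. Device-related events are a subset, so e would be no higher and the overstatement at a given r no larger.

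**The case against.** **The events are captured.** AEs are reported from enrolment for every patient (protocol 9.1.4), and the committee adjudicates SAEs and may review eligibility deviations. This stands: the problem is the endpoint denominator and numerator, not data collection. A reader might infer that these events never appear in any table or listing. The documents do not support that, because SAP 7.0 and 9.0 have no content in the text available, so a listing or supplementary table cannot be ruled out.

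**The direction of bias is not general.** This also stands. In Appendix A only Exclusions 1 and 3 are justified by safety of the device; most other criteria concern consent, scope, indicated use or follow-up. For de novo iliac disease, protocol 1.1 reports 100% technical success and 96.7% nine-month primary patency, so dropping such patients could make results look worse. SAP 5.0 asks whether breaches carry extra risk and does not say that they do.

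**The 280 could mean eligible implanted patients.** Protocol 3.1 also says that patients may be enrolled if all criteria are met. That reading is possible but not stated. It leaves open what happens when a patient counted among the 280 is later found ineligible, and 10.3.2 itself presupposes that some enrolled patients may not qualify.

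**Late exclusion is not shown to be common.** Correct. Several criteria turn on intent or knowledge at consent, so later events do not by themselves create a breach. The emergency consent route makes exclusion after the outcome possible; nothing says how often.

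**Making all treated patients primary brings out-of-scope uses into the headline figure.** This is a fair cost, which separate reporting of those uses can limit.

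**Conclusion.** The concern holds in a limited form. The exclusion is explicit, covers the SAE and death endpoints, and conflicts with the statement that the first 280 implanted patients will be evaluated. No all-treated set or replacement rule appears in the available text.

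The likely effect is small: 0 to 1.3 points of overstated freedom from SAE, inside the 3.06-point half-width. It is zero if ineligible patients have the same risk. The range rests on assumed breach rates of 2% to 10%, assumed relative risks of 1 to 3, and the use of 93.6% as the eligible-patient figure. Optimism is plausible for breaches of safe-use criteria and uncertain for breaches of scope criteria.

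Two stronger readings are not supported. One is that the registry's results are necessarily biased towards the device. The other is that the sample size no longer delivers its precision, since at the planned rates the margin stays near 3 points or below. The plan should still be changed, because the data are already collected and the conflict is easy to remove.

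**What to change.** - In protocol 4.1 and 10.3.2 and in SAP 6.0 ii, define the population for the primary and all safety endpoints as every consented patient treated with the VBX Stent Graft, whether or not an eligibility breach is found.
- Show the criteria-compliant subset alongside as a sensitivity analysis.
- Report the number of eligibility breaches and the reason for each, with out-of-scope uses such as de novo iliac disease shown separately.
- Reconcile protocol 3.1 and SAP 2.0 with these sections, so that it is clear whether the 280 are all implanted patients or only eligible ones, and whether ineligible patients are replaced.

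The cost is wording in both documents and one extra run of the endpoint tables, with no new data. The headline figure may become slightly less favourable, and the all-treated figure will contain a few out-of-scope uses if any occur.
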